#### **12.5 Premature study discontinuation due to adverse event**

In the case of premature study treatment discontinuation due to an adverse event, the Investigator must immediately notify the medical monitor by phone or email and the monitoring team using the specific e-CRF form. The sponsor or designee will inform the authorities.

## 12.6 Safety follow-up

- The Investigator should take all appropriate measures to ensure the safety of the subjects. All patients presenting with any AE should be followed up until normalization or the return to baseline conditions. Follow up may continue after the end of study visit (V6).
- In case of severe laboratory abnormalities, abnormal ECG, the test should be immediately repeated to confirm the value. If confirmed, the treatment should be discontinued and all appropriate measures should be taken to ensure the safety of the patient.

## 12.7 Unblinding procedure

In case of an emergency, the Investigator can unblind the treatment for a specific patient through IWRS that will be available 24h/24h and 7days a week.

Unblinded subjects must be discontinued from the study.

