### 9.3 Description of blinding methods

The SENS-401 and placebo tablet are identical.

Two lists of randomisation using a 1:1:1 randomisation ratio will be generated for the whole study, one for the French sites involved in the ancillary study and one for all the other sites globally, including French sites not participating in the ancillary study.

During Part 1, the 3 treatment arms will be used. During Part 2 the 3 treatment arms will continue to be allocated until one active dose is selected. After dose selection, only the placebo and the selected active dose will continue to be allocated.

The lists of randomisation will be generated centrally, and the investigator, the sponsor study team, the CRO or subjects will be blinded to the Investigational drug administration. The lists of randomisation will be stratified by the duration of the disease at baseline ( $\geq 24$  hours or  $< 24$  hours) and oral corticosteroids intake at baseline (no, yes).

Pharmacokinetic parameters that could potentially unblind the study team will not be disclosed during the conduct of the study.

Investigators will have no access to the randomisation code except under special circumstances. In case of an emergency, when knowledge of the randomisation status is deemed necessary for the medical care of the patient, the randomisation code can be unblinded for a specific patient (see section 11.3.4).

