## 11 STUDY PROCEDURES

### 11.1 Visits

Study procedures are described in the flow chart (Section 4). The following are general guidance relating to all visits.

Every attempt should be made to complete the follow-up visits during the defined window periods.

A final follow-up visit is required for all patients. In the rare cases the End of Study Visit (V6) cannot occur, any attempt to contact the patient should be recorded on a special contact form, until/unless appropriate information is obtained which will allow completion of final follow-up visit in the e-CRF, even after the anticipated timeframe.

Blood is collected by venipuncture. The exact time of sample collection should be transferred into database and should be collected on the laboratory request form for local blood sampling.

Important note: Any abnormal laboratory value, abnormal ECG parameter, SAE will be immediately rechecked for confirmation before making a decision of permanent discontinuation of IP for the concerned patient.

Patients will be advised to avoid skin exposure to strong sunlight and to wear sunglasses in bright sunlight for the duration of the study and for 1 week after the last dose.

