### 11.3 Subject withdrawal

#### 11.3.1 Removal of subjects from therapy or assessment

In accordance with the current revision of the Declaration of Helsinki and current law, a subject has the right to withdraw from the study at any time for any reason without prejudice to his/her future medical care by the physician or at the institution. The Investigator and Sponsor also have the right to withdraw subjects from the study in the event of intercurrent illness, adverse events, treatment failure, protocol violation, or other reasons. Should a subject (or a subject's legally authorized representative) decide to withdraw, all efforts will be made to follow the patient and to complete and report the observations as thoroughly as possible on the appropriate case report form.

Subjects who discontinue treatment should be assessed in accordance with the assessments/tests specified normally for the end of study visit (V6) if discontinuation occurs after Visit 5 or the end of Treatment Visit (V5) if discontinuation occurs before Visit 5.

Subjects who have been withdrawn from the study cannot be re-included in the study. Their subject number and treatment number must not be re-used. They should not be replaced.

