#### 11.3.2 Withdrawal criteria

The subjects could withdraw from the study if they decided to do so, at any time and irrespective of the reason, or this could be the Investigator's decision. All drops out must be documented and the investigator must give the reason (adverse event, subject request, other reason...).

All adverse events, both serious and non-serious, that result in the subject's withdrawal from the study (either by subject request or Investigator decision) must be reported to the CRO (Sensorion designee) within 24 hours for serious events, and within 7 days for non-serious events.

Subjects may be removed from the study by the investigator or the sponsor, if one or more of the following occurs:

- Any serious or severe (CTCAE GRADE 3) related adverse event will lead to permanent treatment discontinuation
- Adverse events of lesser grade should be evaluated in the context of concomitant clinical and laboratory findings and, in the judgment of the Investigator and responsible medical officers, may be cause for temporary or permanent discontinuation of treatment for an individual subject. If interruption of treatment for an individual subject is required due to adverse events more than once during the trial, then the subject will be withdrawn from further treatment.
- Significant laboratory abnormalities
  - Confirmed ALT > 5 ULN (or > 3 times baseline value if ALT > ULN at baseline) or in case of confirmed ALT >3 ULN and total bilirubin >2 ULN (unless the patient has Gilbert's disease documented by genetic testing)
  - Confirmed, non-rapidly reversible, increase in serum creatinine  $\geq$  1.7 mg/dL (150  $\mu$ mol/L) or rapid decrease in creatinine clearance reaching < 50 ml/min-
  - Confirmed rhabdomyolysis (CPK should be controlled in case of suspicion)
  - Confirmed decline in hemoglobin of > 3 g/dL compared to baseline and hemoglobin

level grade 1 (< LLN - 10 g/dL) or higher of CTCAE terminology

- Confirmed platelet count < 100,000 cells/mm^3 with or without spontaneous bleeding
- Confirmed decline in total white blood cell count of > 50% compared to baseline and white blood cell count grade 1 or higher of CTCAE terminology (< LLN - 3000/mm^3)
- Confirmed neutrophil count < 1500/mm^3 with or without signs of infection
- Confirmed decline in lymphocyte count of > 50% compared to baseline and lymphocyte count grade 2 (< LLN - 500/mm^3) or higher of CTCAE terminology

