- Confirmed elevated INR grade 3 (> 2.5 x ULN) or higher of CTCAE terminology
- Confirmed QTc > 500 ms

Note: Any abnormal laboratory value or ECG parameter will be immediately rechecked for confirmation before making a decision of permanent discontinuation of IMP for the concerned patient.

- Any adverse events, per investigator judgment, that may jeopardize the patient safety
- Any patient with a temporary discontinuation for safety reasons that is greater than or equal to 10 consecutive days from last IMP administration
- Any treatment unblinded by the Investigator
- Noncompliance with study protocol by the subject.

Decision by the Investigator or Sponsor that termination is in the subject's best medical interest or administrative decision for a reason other than that of an adverse event.

- Request for withdrawal by the subject for reasons other than an intolerable adverse event.
- Lost to follow-up: For subjects considered lost to follow-up, the e-CRF must be filled in up to the last visit performed. The Investigator should make every effort to re-contact and to identify the reason why the subject failed to attend the visit and to determine his/her health status.

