### 13.3 Analysis populations

#### **13.3.1 Efficacy populations**

##### **13.3.1.1 Intent-to-Treat**

The intent-to-treat (ITT) analysis set will comprise all randomised patients according to randomisation group. All efficacy analyses will be performed on the ITT analysis set.

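### Protocol 12.7, 11.3.2 and 11.1 disagree on whether an emergency-unblinded patient stays in follow-up, so an ITT patient can lose the Day 28 or Day 84 audiogram

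*Protocol*

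**What the plan says.** Protocol 12.7 allows the investigator to break the code for one patient in an emergency and then says "Unblinded subjects must be discontinued from the study". Section 9.3 describes the trigger: "In case of an emergency, when knowledge of the randomisation status is deemed necessary for the medical care of the patient". It does not require the emergency to be related to study drug.

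Other passages bear on the same patient:

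- Protocol 11.3.2 opens its list with "Subjects may be removed from the study by the investigator or the sponsor, if one or more of the following occurs", and one of the items is "Any treatment unblinded by the Investigator".
- Protocol 11.1 says "A final follow-up visit is required for all patients", with no exception for unblinded patients.
- Protocol 11.1.6 applies the Visit 6 procedures, pure tone audiometry included, at premature withdrawal. Section 11.3.1 asks for the Visit 5 or Visit 6 tests when treatment is stopped, depending on timing. For a subject who decides to withdraw, it adds that "all efforts will be made to follow the patient and to complete and report the observations as thoroughly as possible".
- Protocol 13.3.1.1: "The intent-to-treat (ITT) analysis set will comprise all randomised patients according to randomisation group". SAP 6.1.1 agrees.
- SAP 6.2.16 assigns any assessment, scheduled or not, to a visit by study day: Days 20 to 36 count as Day 28, and Days 60 to 108 as Day 84.
- SAP 6.12.2 fits a repeated-measures model under missing at random. SAP 6.12.3 adds copy-reference imputation for Days 7, 14 and 28.

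Protocol 9.3 and SAP section 5 both send the reader to protocol 11.3.4 for emergency unblinding, but 11.3.4 deals with the investigator stopping the research. Neither document says how data collected after unblinding are to be handled.

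**The concern.** A site that has just broken the code gets three different signals: the patient must leave, the patient may be removed, and every patient has a final visit. A site that follows 12.7 literally performs exit tests and cancels the remaining scheduled visits. The patient is still counted in the ITT set, so whatever was not measured becomes missing data in the primary or the Day 84 analysis.

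This missingness is set off by a medical emergency, which may be related to treatment or to the patient's course. Missing at random is therefore harder to defend for these patients than for someone who, say, moves away. The loss is also avoidable, because the visits are already scheduled and the patient may be able to attend. Day 84 PTA is fourth in the SAP's testing order (6.12.6) and lies outside the copy-reference analysis. Part 1 states no dropout allowance: the step from 35 to 37 per arm is attributed to the group sequential looks, so every lost Day 28 value reduces the planned information.

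**Working it through.** **1. Which outcomes can be lost.** Apply the SAP 6.2.16 windows to the day of the exit audiogram, reading 12.7 literally.

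| Exit audiogram (Study Day) | Day 28 value | Day 84 value |
|---|---|---|
| Before Day 20 | missing (Days 10-18 count as Day 14; Day 19 falls in no window) | missing |
| Days 20-36 | supplied by the exit audiogram | missing |
| After the Day 28 visit, before Day 60 | already collected | missing |
| Day 60 or later | already collected | supplied by the exit audiogram |

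The primary outcome is at risk only for an exit before Day 20. Day 84 is at risk for any exit before Day 60.

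**2. The plan's own sample size.** The inputs from protocol 13.1 are a difference of 15 dB, SD 30 dB, baseline correlation 0.45, one-sided 5% and, from SAP section 4, 75% power.

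- Adjusted SD = 30 × √(1 − 0.45²) = 26.79 dB, the value given in protocol 13.5.1.
- n per arm = 2 × (1.645 + 0.674)² × (26.79/15)² = 34.3, rounded up to 35, or 105 in three arms. This reproduces the plan's fixed-design figure.
- Part 2 (10 dB, SD 20 dB, two-sided 5%, 90% power) gives 85 per arm, and 85/0.90 = 94.4, rounded up to 95. This also agrees.

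**3. Size per affected patient, Part 1.** One patient is 1/37 = 2.7% of an arm. Let D be the amount by which the patient's true Day 28 change is worse than the model predicts. The documents give no value, so D is assumed to be 20 dB, with a range of 10 to 40 dB. The arm mean is off by about D/37:

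- 10/37 = 0.27 dB
- 20/37 = 0.54 dB
- 40/37 = 1.08 dB

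The standard error of the difference between two arms is about 26.79 × √(2/37) = 6.2 dB. One patient therefore moves the estimate by about 4%, 9% or 17% of a standard error. The shift flatters the active arm if the patient was on active drug and flatters placebo if the patient was on placebo.

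**4. Power if Day 28 values are lost.** These are fixed-design normal approximations that ignore the group sequential looks. The loss rates are assumed. Part 2 losses are taken on top of the planned 10% dropout.

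| Assumed loss | 0% | 1% | 2% | 5% | 10% |
|---|---|---|---|---|---|
| Part 1, 37 per arm | 77.7% | 77.4% | 77.0% | 75.9% | 73.9% |
| Part 2, 95 per arm | 90.5% | 90.2% | 89.8% | 88.8% | 86.9% |

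At loss rates of 1% or 2% the change is under one percentage point in either part.

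**The case against.** The case against has several parts, and much of it stands.

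- A reader might infer from 12.7 that every unblinded patient loses both Day 28 and Day 84. The documents do not support that. Exit audiometry is required, and the windows let it count when it falls on the right days. Unblinding after Visit 5 leaves Day 28 untouched.
- A reader might infer that safety follow-up ends. It does not. Protocol 12.4.1 and 12.6 follow adverse events to outcome, possibly beyond Visit 6, and 12.4.2 requires serious events to be reported for 30 days after the last treatment day. Only the remaining scheduled visits are in doubt.
- A reader might infer that the data are missing because of treatment. The trigger is an emergency, so a link with treatment is plausible but not stated.
- The contradiction can be read more mildly. The optional wording in 11.3.2 is a general lead-in that also covers an item worded as mandatory, and a Visit 6 assessment performed at withdrawal could be taken to satisfy 11.1. The protocol also uses study and treatment discontinuation loosely: the heading of 12.5 names one and its text the other. These readings are possible, but a site has no means of choosing among them, which is why the text needs attention.
- The primary model uses the patient's own baseline and any Day 7 or Day 14 values, and the copy-reference analysis tests departures from missing at random at Days 7 to 28. This softens the problem for the primary endpoint but leaves Day 84 uncovered.
- Audiometry is a subjective test, and the same audiologist normally retests each patient. Keeping audiograms after unblinding exchanges missing data for possible assessment bias. This is a genuine cost, and the proposed change has to deal with it.

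**Conclusion.** The passages conflict as written and should be reconciled. The supportable conclusion is limited: an ITT patient who is unblinded and leaves before Study Day 20 has no clear route to a Day 28 value, and one who leaves before Day 60 has none to a Day 84 value. The reason for the loss may be informative.

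The expected effect is small. For each affected patient it is about 0.3 to 1.1 dB in a Part 1 arm mean, against a planned difference of 15 dB and a standard error near 6.2 dB. That rests on an assumed shortfall of 10 to 40 dB, 37 patients per arm, and a loss confined to one arm. The number of unblindings is not given, and the total effect scales with it. No sample-size figure changes. This is a worthwhile low-cost improvement, not a threat to the trial's conclusion.

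**What to change.** **Protocol.** In 12.7 and the matching item of 11.3.2, state that unblinded subjects remain in follow-up for the scheduled assessments, including Day 28 and Day 84 audiometry, and that the date and reason of unblinding are recorded. This also brings both passages into line with 11.1. Correct the reference to 11.3.4 in protocol 9.3 and SAP section 5. What unblinding means for study drug must also be made consistent between 12.7 and 11.3.2; no position is taken here on what it should be.

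**SAP.** Keep audiograms taken after unblinding in the ITT analysis, flag them in the listings, and add a sensitivity analysis that sets them to missing. The third sensitivity analysis in 6.12.3 already sets audiograms after rescue therapy to missing, so the programming is familiar. The new analysis would stop at that step, without the baseline imputation used for rescue.

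**Cost.** A few sentences of protocol and SAP text and one further sensitivity analysis. The downside is that a few audiograms will no longer be blind; the flag and the sensitivity analysis show whether they matter.

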## 12.8 General Safety Monitoring

### 12.8.1 Data Monitoring Committee

An external data monitoring committee (DMC), consisting of two or more physicians and a statistician, independent from the sponsor and the monitoring team will be set up to review the safety of the product throughout the conduct of the study, as well as the efficacy when the last (Day 28) visit of Part 1 is reached or if an interim GST look recommends premature discontinuation of Part 1.

Safety data will be provided by patient with relevant information according to the DMC charter that will be established before the first patient is included. The first review is expected to be done after 30 patients have completed the study.

The DMC will meet regularly to review the blinded safety information as follows:

- The number of screened and included patients and demography (gender, age)
- The total number of AEs and SAE per treatment groups, displayed by preferred term.
- The ECG database provided by central reader
- The clinically significant abnormal laboratory values

In addition, the DMC members will receive the EDC SAE alerts by email that are automatically triggered when a site enters a SAE in the eCRF. The PV representative will provide each SAE blinded report for this study to the DMC members for their consideration within 7 days in case of fatal or life threatening events or within 15 days in case of other SAEs from the time Drug Safety has received the report.

In case of SUSAR or any other relevant SAE, the DMC will re-evaluate the risk for the patients to allow or not the continuation of the study.

The final list of adverse events to be reviewed will be discussed and finalized by the DMC members during the kick off meeting prior to the start of the study and appended to the signed DMC charter. It will be sent upon request to European or National authorities. During Part 1, two interim efficacy looks are planned. They will be performed by an independent statistician dedicated to the Group Sequential Test (GST) (see section about Possible changes during Part 1). Each of these interim looks will lead to an automatically generated recommendation to the sponsor of continuing the study for efficacy or futility respectively.

The committee will review the results and will provide further recommendation to the sponsor for stopping Part 1 for efficacy or futility or continuing the study as planned, until the next look or the final analysis of Part 1.

No information about these results will be communicated to investigators and the International Coordinating Investigator until the study is completed or discontinued.

The committee will be responsible for selecting the active dose to be tested in Part 2. The committee will be provided with the unblinded efficacy data on the primary end-point when 111 patients randomised to Part 1 have completed the 4-week treatment. The DMC may also recommend to modify the sample size of the Part 2 study.

## 13 STATISTICAL CONSIDERATIONS

The two parts of the study (Part 1 and Part 2) will be analysed separately.

The statistical considerations summarized in this section outline the plan for data analysis of this study. A statistical analysis plan (SAP) will be finalized prior to the database lock.

For continuous variables, descriptive statistics will include at least the following: the number of patients reflected in the calculation (n), mean, median, standard deviation, minimum, and maximum.

For categorical data, frequencies and percentages will be displayed for each category.

All statistical analyses will be displayed on total population and on the 2 subgroups: non-ancillary study sites and ancillary study sites.

SAS Version 9.4 or later will be used for statistical programming.

### 13.1 Determination of sample size

The sample size is based on the primary end-point: average change in air conduction derived from PTA in dB between the baseline and week 4 (Day 28±3d) on the 3 most affected contiguous frequencies.

Part 1: A sample size of 111 patients (37 patients per treatment arm) was retained corresponding to following assumptions:

- Each comparison to placebo performed at 5% one-sided significance level (with higher dose to be tested first and low dose to be tested conditionally to the high dose significance).
- Power of each comparison to placebo set to 75.75%.
- Randomisation ratio 1:1:1.
- Intra-group standard deviation of 30 dB is estimated based on recent publication in SSNHL with other pharmaceutical therapies and blinded examination of variance (a 0.45 correlation between Day 28 and baseline).
- A difference to placebo of 15 dB is expected, which would be considered clinically meaningful.
- The corresponding fixed design sample size of 105 patients (35 patients per treatment arm) was then inflated to 111 patients (37 patients per treatment arm) to allow the use of a GST design with 3 looks (2 interim looks and a final look).

This design of Part 1 was introduced in the protocol amendment leading to version 4.0. The revised assumption of the intra-group standard deviation (adjusted for baseline) of 30 dB was based on a blinded review of the variability of 63 patients, which led to an estimate of the adjusted standard deviation more in line with the 27 dB seen in a recent publication in SSNHL (52) than with the 20dB seen in the publication used at time of the protocol initiation (53). The choice of the power level and of the significance level, combined with the strategy of testing the low dose conditionally after the high dose, was guided by the unexpected low recruitment rate observed in the study. The 3-look GST design (interim looks plus one final part 1 analysis) was introduced in order to allow an early discontinuation (for futility or for efficacy) of Part 1. The first GST look was performed and the outcome was a recommendation to continue Part 1 in the absence of crossing of any boundary.

Part 2: A sample size of 190 patients (95 patients per treatment arm) was retained corresponding to following assumptions:

- Comparison to placebo performed at 5% two-sided significance level
- Power of the comparison to placebo set to 90%.
- Randomisation ratio 1:1
- Intra-group standard deviation of 20 dB is estimated based on recent publication in SSNHL with other pharmaceutical therapies.
- A difference to placebo of 10 dB is expected as considered clinically meaningful
- 10% dropout rate

The sample size of Part 2 will be re-estimated based on Part1 results when available. The final sample size will be submitted for approval to competent authorities prior to the pivotal part start

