## **Statistical methods**

### **Sample Size Calculation**

The sample size is based on the average change in PTA in dB between the baseline and week 4 in each part of the study.

**Part 1:** A sample size of 111 patients (37 patients per treatment arm) was retained corresponding to following assumptions:

- Each comparison to placebo performed at 5% one-sided significance level (higher dose to be tested first and low dose to be tested conditionally to the high dose statistical results)
- Power of each comparison to placebo set to 75%.
- Randomisation ratio 1:1:1
- Intra-group standard deviation of 30 dB
- Difference to placebo of 15dB.
- Corresponding fixed sample size design of 105 patients (35 patients per treatment arm) inflated to 111 patients (37 patients per treatment arm) to allow the use of GST design with 3 looks (2 interim and 1 final look)

**Part 2:** A sample size of 190 patients (95 patients per treatment arm) is retained corresponding to following assumptions:

- The comparison to placebo performed at 5% two-sided significance level
- Power of the comparison to placebo set to 90%.
- Randomisation ratio 1:1
- Intra-group standard deviation of 20 dB
- Difference to placebo of 10 dB.
- 10% dropout rate

The sample size of Part 2 will be re-estimated based on Part 1 results when available.

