3-During this same blinded examination, the distribution of the D28 primary endpoint data (residuals and predicted value, from a simplified model of D28 data including D0 data as one of the covariates) will also be graphically inspected to determine whether a logarithmic transformation of the data would be appropriate. If such a transformation is retained, the statistical analysis plan will be amended accordingly before the interim analysis. 4-Two interim GST looks will be performed during Part 1 of the study, which may lead to early discontinuation of Part 1 for futility or efficacy.

The GST design was defined with a 75% power for a standardized difference of means of 0.546 (15/26.79), an overall 5% one-sided significance level (with a gamma function of parameter - 2 as alpha spending function) and a binding futility procedure (with a gamma function of parameter -4 as beta spending function). At each GST look, the z-score statistic will be calculated for the estimated difference of high dose versus placebo. The GST looks are planned for 41 (first GST look), 55 (second GST look) and 74 (final analysis of Part 1) patients available for the high dose and the placebo together. The GST design can be summarized as follows:

Analysis stage	Futility		Efficacy	
	nominal p-value limit	z-score limit	nominal p-value limit	z-score limit
Anticipated cumulative number of subjects in high dose + placebo				
N = 41	≥ 0.6345	≤ 0.344	≤ 0.075	≥ 2.432
N = 55	≥ 0.8047	≤ 0.859	≤ 0.150	≥ 2.170
N = 74	≥ 0.9500	≤ 1.645	≤ 0.0500	≥ 1.645

In this GST design, the first interim look, second interim look and final analysis are planned when 63, 85 and 111 patients, respectively (when 41, 55, 74 patients can be expected in the high dose and placebo groups) have been randomized up to the date still theoretically compatible with reaching Day 28 and having the data centrally reviewed before he considered GST look. However, irrespective of the actual number of patients in high dose and placebo observed in the GST look, the z-score limits for futility and efficacy will be used without any change.

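### The 75% power given for each Part 1 comparison is the power of a single pairwise test; under the fixed sequence a confirmatory low-dose result has about 60–66% power

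*Protocol*

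**What the plan says.** Protocol 13.1 lists the Part 1 sizing assumptions. The first is "Each comparison to placebo performed at 5% one-sided significance level", qualified in brackets by "with higher dose to be tested first and low dose to be tested conditionally to the high dose significance". The next reads "Power of each comparison to placebo set to 75.75" percent. The protocol synopsis (section 3, Sample Size Calculation) has "Power of each comparison to placebo set to 75" percent, and SAP section 4 also gives 75%. A single effect size serves both doses: "A difference to placebo of 15 dB is expected, which would be considered clinically meaningful".

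The gate is binding. Under protocol 13.5.1 (Final analysis of Part 1) and SAP 6.12.2 (Analysis of Part 1), the low-dose p-value is only exploratory if the high dose is not significant.

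The group sequential design in protocol 13.5.1 and SAP section 7 is defined at 75% power, and its looks concern high dose versus placebo only. SAP sections 4 and 7 add that the first look crossed no boundary, the second was not performed, and the final look is replaced by a test at the same one-sided 0.0500 boundary.

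Neither document gives a power for the low dose under the sequence, or says that 75% is a marginal figure.

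**The concern.** The power statement and the gating rule sit in adjacent bullets, and protocol 13.1 says the power level was chosen together with the conditional testing strategy. A reader will naturally take 75% as the power of that strategy for both doses. For the low dose it cannot be, because success requires the high-dose test to succeed first.

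What is at stake is interpretation. Determining the dose effect is a secondary objective. A low-dose result that fails, or is exploratory because the gate closed, would be read as coming from a test with a 25% chance of missing a true 15 dB effect. Under the stated procedure that chance is roughly 34–40%.

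**Working it through.** **Inputs**
- One-sided alpha 0.05 (critical z = 1.645), 1:1:1 allocation, 15 dB difference, 35 per arm fixed or 37 per arm with the sequential design: protocol 13.1.
- SD: "Intra-group standard deviation of 30 dB is estimated based on recent publication in SSNHL", with "a 0.45 correlation between Day 28 and baseline". Adjusted SD = 30 × √(1 − 0.45²) = 26.79 dB, the value printed in protocol 13.5.1 and SAP section 7.
- Looks at 41, 55 and 74 patients (high dose plus placebo), efficacy z 2.432 / 2.170 / 1.645, binding futility z 0.344 / 0.859 / 1.645: protocol 13.5.1.
- Correlation between the two test statistics: 0.5, which follows from a shared placebo arm of equal size.
- Assumptions of mine: a true 15 dB effect at both doses (the documents give one difference, not split by dose) and no dropout (none is stated for Part 1).

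**Step 1. Reproduce the plan's figure (one comparison)**

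At 35 per arm, SE = 26.79 × √(2/35) = 6.40 dB and 15/6.40 = 2.342. Power = Φ(2.342 − 1.645) = Φ(0.697) = 75.7% (75.0% with the t distribution). The sample-size formula returns 35 per arm for 75%. The unadjusted SD of 30 would need 44 per arm, so the sizing used 26.79. A simulation of the printed boundaries (1 million runs) gives high-dose power 76.1% and type I error 5.0%. The stated figure is therefore right for the high dose.

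**Step 2. Low dose under the sequence, without interim looks**

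Power = P(Z_H > 1.645 and Z_L > 1.645), bivariate normal, correlation 0.5.
- 35 per arm, both means 2.342: 63.0%.
- 37 per arm: SE = 26.79 × √(2/37) = 6.23 dB, both means 2.408: 65.6%. The single-comparison power here is 77.7%.

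**Step 3. Low dose under the sequence, with the printed boundaries**

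| Design | Low dose tested at the look where the high dose wins | Low dose tested on the full 37 per arm |
|---|---|---|
| Three looks (protocol) | 60.1% | 64% |
| Look 1 plus one final test (SAP) | 62.2% | 65% |

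The two columns reflect an ambiguity: protocol 13.5.1 places the low-dose test under the final analysis of Part 1, but lets it follow from a significant interim look. These are design-stage probabilities, not conditioned on the known outcome of look 1.

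**Step 4. Sensitivity**
- Smaller low-dose effect (35 per arm, no interim looks, high dose at 15 dB): 51% at 12 dB, 42% at 10 dB.
- The documents print a standardized difference of 0.546, although 15/26.79 = 0.560. With 0.546 and testing at the stopping look, the low-dose figure is 57.9% (three looks) or 60.0% (look 1 plus final).

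**The case against.** The strongest reply is that the documents make no arithmetical error. Power of a comparison, listed among sizing assumptions, ordinarily means the marginal power of one two-group test, and on that reading 75% is correct for the low dose too. Sizing each pairwise test this way under a fixed sequence is common. Given a significant high dose, the low-dose success rate is above 75%: 0.630/0.757 = 83% at 35 per arm. The conditional strategy is also disclosed, with its motive of slow recruitment. All of this stands, and it limits the point to an unlabelled figure and a missing one. It does not remove the point, because neither document says the 75% is marginal or gives the low-dose power under the procedure it prescribes.

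A reader might infer that the Part 2 dose choice is compromised. The documents do not support that. The data monitoring committee selects on unblinded benefit/risk at each dose (protocol 7.2 and 7.3), not on the gate. The low-dose p-value is reported either way (SAP 6.12.2), with 90% intervals for the comparisons (SAP 6.12), and high versus low dose is a separate exploratory contrast.

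A reader might also settle on a flat 60%. That fits only the three-look design with the low dose tested at the stopping look, and the SAP has since dropped looks two and three. Figures near 50–52% arise if SD 30 is used, but the 35 per arm does not rest on that value. Squaring the power, 0.75² = 56.3%, ignores the shared placebo arm.

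**Conclusion.** The point holds in a limited form. The stated 75% is the procedure's power for the high dose and only a marginal power for the low dose. The probability of a confirmatory low-dose result is about 63% in the fixed design, 60–64% in the protocol's three-look design, and about 62–66% as the SAP now runs Part 1 (look 1 then one final test, or a single test at 37 per arm). That is some 9 to 15 points below 75%.

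These figures assume that the low dose works as well as the high dose and that nobody drops out. Both assumptions favour the plan, so a weaker low dose or missing Day 28 data would lower them. They also use the adjusted SD of 26.79; taking the printed 0.546 at face value lowers the sequential figures by about two points. The consequence is confined to reading a non-significant or exploratory low-dose result.

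**What to change.** In protocol sections 3 and 13.1 and SAP section 4:
- State that 75% is the power for high dose versus placebo, being the marginal power of a single comparison.
- Use one value in place of 75% and 75.75%.
- Add that the power for a confirmatory low-dose result under the fixed sequence is about 60–66% in the protocol, and about 62–66% in the SAP for the design as now run.
- List the assumptions beside it: 15 dB at both doses, adjusted SD 26.79, 1:1:1 allocation with a shared placebo arm, no dropout, and whether the low dose is tested on the data at the stopping look or on all Part 1 patients.

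The cost is a sentence or two in each place and a less favourable published figure. No sample size, boundary, test or decision rule changes.
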